1.4 Dose Rationale

1.4.1 Dose for PK Assessment

The dose used for PK assessment, i.e., 50 ± 5 IU/kg, is in line with the current recommendations of the *Guideline on the clinical investigation of recombinant and human plasma-derived factor VIII products* (EMA/CHPM/BPWP/144533/2009), which recommends a dose of 25–50 IU/kg. It is expected that this dose will result in measurable FVIII:C plasma concentrations after 48 hours in most, if not all, patients.

The \pm 5 IU/kg range (rather than a fixed dose) was included to allow the entire contents of reconstituted vials to be injected rather than taking out an exact volume, which is difficult technically and might result in dosing errors.

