6.1.2 PK Visit

Patients will receive *Wilate* at a dose of 50 ± 5 IU/kg (labelled dose) after a washout period of at least 72 hours from their last FVIII injection. Patients must not be experiencing any bleeding.

The following assessments will be performed:

- Body weight before injection
- Blood samples will be taken for the following purposes and at the following time points:
 - FVIII:C plasma concentration (OS and CHR) for PK assessment within 1 h before injection and 15±5 min, 1 h (±5 min), 6 h (±30 min), 24±2 h, and 48±2 h after the end of injection
 - Safety laboratory before and 48±2 h after injection
 - **FVIII inhibitor** before injection
 - Plasma VWF:Ag and VWF:Ac within 1 h before injection and 15±5 min after the end of injection
- Vital signs before injection as well as 1 h (±5 min) and 48±2 h after injection
- AE monitoring
- Concomitant medications

At the end of this visit, patients will **receive a patient diary**. The Investigator will explain to the patient how to fill in the diary and emphasize the importance of carefully documenting all treatment details, AEs, and concomitant medications. Also, patients will be **provided with IMP** for home treatment. They will be re-supplied whenever necessary during the study.

The first prophylactic injection of *Wilate* after the PK Visit marks the beginning of the Prophylactic Treatment Phase.

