7.2.1 Pharmacokinetic Evaluation

The following PK parameters for FVIII:C will be determined using a non-compartment model:

- AUC_{norm} and AUC
- In vivo half-life (T_{1/2})
- Maximum plasma concentration (C_{max})
- Time to reach maximum plasma concentration (T_{max})
- Mean residence time (MRT)
- Volume of distribution (Vd)
- Clearance (CL)
- Incremental in vivo recovery (IVR)

For details on the laboratory analyses, see Section 7.3.5.

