- [3] Before injection as well as 48 ± 2 h after injection [**local laboratory**]
- [4] Before injection as well as 15 ± 5 min after injection
- [5] Blood sampling within 1 h before injection and 15 ± 5 min, 1 h (± 5 min), 6 h (± 30 min), 9 ± 1 h, 24 ± 2 h, and 48 ± 2 h after the end of injection [**central laboratory**]
- [6] Blood sampling within 1 h before injection as well as 15 ± 5 min after the end of injection [**central laboratory**]
- [7] If first sample was negative for parvovirus B19 antibodies (sample to be taken before injection) [**central laboratory**]
- [8] CD4+ count to be repeated if interval between Screening Visit and first injection exceeds 30 days. To be included into the study, the patient's CD4+ count must be $>200/\mu\text{L}$ (i.e., inclusion criterion no. 4).
- [9] Unless obtainable from patient's medical history
- [10] Blood sampling for inhibitor testing should preferably be done at the time of trough FVIII:C levels [**central laboratory**]
In case of positive inhibitor results, inhibitor retesting using a second, separately drawn sample should be performed, preferably within 15 days of becoming aware of the positive result.
- [11] Documentation of any thromboembolic events only (to be documented on AE page)

| | |
|----------------------------------|---------------|
| STATISTICAL ANALYSIS PLAN | |
| Protocol No: WIL-30 | |
| Version Number: 1.2 | Page 13 of 27 |
| Date of Issue: 2019-07-08 | |

FLOW CHART OF ASSESSMENTS FOR SURGICAL PROPHYLAXIS

| | Within 12 hours before start | Within 3 hours before start | Surgery | | POP day 1 | Any POP day | End of POP period | 3-8 weeks after surgery | |
|---|-------------------------------|-----------------------------|-------------------|---------|-----------|-------------|-------------------|-------------------------|--|
| | | | Intra-operatively | End [1] | | | | | |
| Body weight | x | | | | | | | | |
| Type of surgery | x | | | | | | | | |
| Location of surgery | x | | | | | | | | |
| Severity of surgery | x | | | | | | | | |
| Expected duration of surgery | x | | | | | | | | |
| Expected average/ maximum blood loss during surgery | x | | | | | | | | |
| Actual duration of surgery | | | | x | | | | | |
| Actual blood loss during surgery | | | | x | | | | | |
| Administration of IMP | | x | (x) | (x) | (x) | (x) | (x) | | |
| FVIII plasma levels | | # | (#) | (#) | # [2] | # | # | | |
| VWF:Ag and VWF:Ac | | # | | | # [2] | # | # | | |

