5 STATISTICAL ANALYSES

All statistical analyses will be performed using SAS[®] for Windows (Version 9.3 or later).

Descriptive statistics will always be given for the entire population.

| | |
|---|---------------|
| 
STATISTICAL ANALYSIS PLAN Protocol No: WIL-30
 | |
| Version Number: 1.2 | Page 16 of 27 |
| Date of Issue: 2019-07-08 | |

The analysis of safety will be based on the SAF set.

Analysis of the PK properties of *Wilate* will be based on the PK set.

For secondary endpoints, FAS and PP analyses will be carried out, unless these analysis sets differ by no more than 1 patient from the FAS.

Analysis of the efficacy and safety of *Wilate* in surgeries will be based on the SURG set.

If not stated otherwise the following standard descriptive statistics will be presented:

Descriptive statistics for continuous data

Number of subjects (N), arithmetic mean, standard deviation (SD), minimum, lower quartile, median, upper quartile and maximum will be presented. Usually mean and quartiles will have 1 decimal more, SD 2 decimals more than the original values (as given with min, max); N has no decimals. These descriptive statistics will be determined for measured values and for differences to baseline.

Descriptive statistics for categorical data

Absolute frequencies (N) will be presented with 0, relative frequencies (%) with 1 decimal. For changes from baseline, shift tables may be generated.

Inferential statistics

If not stated otherwise all statistical tests will be performed as described in the corresponding sections below.

All p-values will be rounded to 4 decimals (p<0.0001 will be displayed, if the p-values are less than 0.0001). Statistical significance will be declared if the rounded p-value will be less than 0.05.

All confidence intervals (CI) will be derived two-sided and at a confidence probability of 1- α = 0.95.

Listings

All subject data will be listed by subject. Identification variable will be the subject ID (composed of study, center and subject number separated by a hyphen, e.g. '30-01-01'). Any derived data listed will also be stored permanently and will be calculated as outlined in section 8.1 of this SAP.

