5.1.2 Missing data

In case of missing weight documentation data will be imputed using the Last Observation Carried Forward (LOCF) approach to calculate the dose per kg body weight (IU/kg). For calculation of PK parameters, missing measurements on a subject's PK profile will be handled according to the algorithms included in the PK software WinNonlin (version 7.0).

No further imputations for missing data will be performed.

Calculations pertaining to the derivation of annual bleeding rates will be based on documented time periods only.

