8 APPENDICES

8.1 Formulas for derived variables

| Variable | Description |
|---|--|
| Actual potency | Potency of IMP (IU) based on central laboratory measurements of FVIII content by two assay methods: CHR (chromogenic) and OS (one-stage). The analysis of PK and IVR assessment will be based on actual potencies |
| Durations between two dates | Later date minus earlier date plus 1, expressed in days. (Remark: Duration will be 1, if both dates are the same.) |
| Spontaneous annualized bleeding rate (SABR) | Number of spontaneous bleedings (excluding bleedings occurring in surgery periods) between first dose of IMP and Study Completion visit (or last dose of IMP in case completion visit not performed) / time under prophylaxis (days)/365.25 (see prophylactic treatment phase) |
| Total annualized bleeding rate (TABR) | Number of bleedings (excluding bleedings occurring in surgery periods) between first dose of IMP and Study Completion visit (or last dose of IMP in case completion visit not performed) / time under prophylaxis (days)/365.25 (see prophylactic treatment phase) |
| Surgery Phase | Last treatment for surgery – first treatment for surgery + 1 |
| Prophylactic treatment phase | Date of completion visit or date of last treatment with IMP in case completion visit not performed) – (date of first prophylactic treatment after the PK visit) + 1 – Surgery phases |
| Time in study | Date of study completion – date of screening +1 |

| STATISTICAL ANALYSIS PLAN Protocol No: WIL-30 | |
|--|---------------|
| Version Number: 1.2 | Page 25 of 27 |
| Date of Issue: 2019-07-08 | |

| Variable | Description |
|---|---|
| Time under treatment | Date of last treatment – date of first treatment + 1 (average drug consumption data will be calculated relative to time under treatment) |
| AUC | Area under the curve from baseline to infinity $AUC = \sum \left(\frac{(C_n + C_{n+1})}{2} \cdot \Delta t \right) + \frac{C_{last}}{K}$ (C_{last} is the last available measurement) |
| AUC _{norm} | AUC normalized for the administered dose |
| AUMC | Area under the moment curve (from baseline to infinity) $AUMC = \sum \left(\frac{(t_n \cdot C_n + t_{n+1} \cdot C_{n+1})}{2} \cdot \Delta t \right) + \frac{C_{last} \cdot t_{last}}{K^2} + \frac{C_{last}}{K}$ |
| CL | Clearance $CL = \frac{D}{AUC}$ where D is the actual dose administered (see remark above) |
| C ₀ | FVIII concentration before IMP administration |

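### The linear trapezoid in SAP 8.1 overstates AUC by about 6–12% and understates clearance by about 6–11% on the Protocol v02 sampling times, if FVIII:C half-life is 8–12 h (assumed)

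*SAP*

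**What the plan says.** SAP v1.2, section 8.1, gives one AUC formula, running from baseline to infinity: "AUC = \sum \left(\frac{(C_n + C_{n+1})}{2} \cdot \Delta t \right) + \frac{C_{last}}{K". The formula is the same in v1.0 and v1.1. CL is dose divided by AUC, MRT is AUMC divided by AUC, and Vd is CL times MRT. The extrapolated part of AUMC is printed with the terms "C_{last} \cdot t_{last}}{K^2} + \frac{C_{last}}{K".

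The listings paragraph of SAP section 5 ties derived data to these formulas: they "will be calculated as outlined in section 8.1 of this SAP". SAP 5.1.2 brings in the PK software only for missing measurements, which are handled "according to the algorithms included in the PK software WinNonlin (version 7.0". No trapezoid option is named there or elsewhere. The protocol is less specific: section 7.2.1 says only that the parameters "will be determined using a non-compartment model".

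Sampling in Protocol 6.1.2 is pre-dose, 15 min and 1 h, then "6 h (±30 min), 24±2 h, and 48±2 h after the end of injection". Legend [5] of the SAP v1.2 flow chart (section 2.4) adds a sample, so that its later times are "9 ± 1 h, 24 ± 2 h, and 48 ± 2 h after the end of injection".

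**The concern.** The linear trapezoid is a recognised non-compartmental rule and does little harm when samples are close together. Here two intervals are 18 and 24 h wide (15 and 24 h if the 9-h sample is taken). A straight line between two points on an exponential decline always lies above the curve. The error therefore has a known direction, does not shrink with more patients, and grows as half-life shortens.

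AUC, AUCnorm and CL belong to the primary endpoint (Protocol 3.1.1) and are presented by age group (Protocol 9.2.2, Subgroup Analyses). Protocol 3.3 gives the difference in FVIII clearance between adolescents and children as the reason for the study. The level of paediatric clearance is thus a main product of this trial, and the formula biases it downwards. T1/2, Cmax, Tmax and IVR do not use the trapezoid and are unaffected.

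**Working it through.** The documents state no AUC, CL or half-life value, so there is no plan figure to reproduce. The check applies the printed formula to a curve whose true AUC is known.

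**Inputs**
- Times after injection: 0.25, 1, 6, 24, 48 h (Protocol 6.1.2); 9 h added for the SAP legend.
- Pre-dose FVIII:C = 0 at time 0 (severe disease, at least 72 h washout). The first interval rises linearly to the 15-min sample.
- C(t) = exp(−Kt), K = ln 2 / half-life. Half-life is **assumed**: 8, 10, 12 h.
- True AUC = 1/K; tail = C(48)/K. Protocol 1.4.1 expects "measurable FVIII:C plasma concentrations after 48 hours in most, if not all, patients".

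**Worked case: half-life 10 h, Protocol v02 times** (K = 0.06931, true AUC = 14.427)

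| Interval (h) | C at start, end | Linear area | Exact area | Error, % of true AUC |
|---|---|---|---|---|
| 0–0.25 | 0, 0.983 | 0.123 | 0.248 | −0.9 |
| 0.25–1 | 0.983, 0.933 | 0.718 | 0.718 | 0.0 |
| 1–6 | 0.933, 0.660 | 3.982 | 3.943 | +0.3 |
| 6–24 | 0.660, 0.189 | 7.643 | 6.785 | +5.9 |
| 24–48 | 0.189, 0.036 | 2.704 | 2.216 | +3.4 |
| tail | – | 0.518 | 0.518 | 0 |

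The linear total is 15.688, and 15.688/14.427 − 1 = +8.7%. For CL, 14.427/15.688 − 1 = −8.0%. Nearly all of the error comes from the two wide gaps.

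**Same calculation across cases**

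| Schedule | Half-life (h) | AUC bias | CL bias |
|---|---|---|---|
| Protocol v02 | 8 / 10 / 12 | +12.3 / +8.7 / +6.4% | −10.9 / −8.0 / −6.0% |
| SAP legend (with 9 h) | 8 / 10 / 12 | +7.7 / +5.9 / +4.5% | −7.2 / −5.6 / −4.3% |
| v02, 48 h not measurable | 8 / 10 / 12 | +8.6 / +5.4 / +3.5% | −7.9 / −5.1 / −3.4% |
| Linear-up/log-down, v02 or SAP legend | 8 / 10 / 12 | −1.1 / −0.9 / −0.7% | – |

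Outside the assumed range, on v02, the AUC bias is +17.7% at 6 h and +4.8% at 14 h.

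**Robustness**
- Starting from a back-extrapolated C0 instead of a pre-dose zero gives AUC +7.1% to +13.3% (12 to 8 h).
- Assumed bi-exponential curves with back-extrapolated C0 give about +7.5% to +16%.
- Simulation with the protocol's sampling windows and an assumed 5% assay CV gives a mean CL bias of −11.0 / −8.2 / −6.1% (linear) and +1.1 / +0.8 / +0.7% (log-down).

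**Age contrast, equal volume assumed.** The estimated CL ratio is the true ratio times the ratio of the AUC biases.
- 8 h against 10 h, true ratio 1.25: 1.25 × 1.087/1.123 = 1.21 on v02; 1.25 × 1.059/1.077 = 1.23 on the SAP legend.
- 8 h against 12 h, true ratio 1.50: 1.50 × 1.064/1.123 = 1.42 on v02; 1.50 × 1.045/1.077, about 1.45, on the SAP legend.

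**AUMC tail.** Integrating t·C(t) beyond t_last gives C_last·t_last/K + C_last/K². The printed terms exchange K and K², and they do not have the same units. At 10 h on v02 the printed tail is 359.1 and the correct one 32.3. The linear AUMC sum up to 48 h is 164.5 and the log-rule sum 175.8. True MRT is 14.4 h.

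| Rule | Printed tail | Corrected tail |
|---|---|---|
| Linear | (164.5 + 359.1)/15.688 = 33.4 h | (164.5 + 32.3)/15.688 ≈ 12.5 h; Vd −20% |
| Log-down | (175.8 + 359.1)/14.302 = 37.4 h | (175.8 + 32.3)/14.302 ≈ 14.6 h; Vd +2% |

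MRT and Vd come out close to the truth only when both changes are made.

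**The case against.** The linear rule is legitimate, fully specified, unchanged through three SAP versions and compatible with the protocol. The size of the bias rests on an assumed half-life and on the wider of two sampling schedules. Protocol v02 is labelled for Ukraine only, and SAP v1.2 also cites Protocol version 03, which is not available here. The analysis is descriptive with no acceptance limit. If between-patient CV were 20–40% (an assumption), the 95% CI half-width for a mean would be about ±17–33% at n = 8 (2.365 × CV/√8) and ±32–64% at n = 4 (3.182 × CV/√4), which is larger than the bias. Finally, changing a primary-endpoint formula after the Database Review Meeting invites criticism. Keeping linear as the main result, with log-down as a sensitivity analysis, would be the cautious order.

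Part of this stands. The schedule that applied to all patients cannot be confirmed, the exact size is conditional, and the late timing is a real cost. The AUMC tail and the 9-h mismatch are separate faults and add nothing to the case against the trapezoid. But both available schedules give a bias in the same direction, and wide intervals do not excuse a systematic error that can be removed. Showing both results with the timing stated answers the prespecification point.

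**Conclusion.** The concern holds. With an assumed half-life of 8–12 h and mono-exponential decline, the SAP formula overstates AUC by about 6–12% and understates CL by about 6–11% on the Protocol v02 times. On the SAP legend times the figures are about 4.5–8% and 4–7%. The direction is secure for any convex decline sampled this sparsely; the size depends on half-life, schedule and whether the 48-h value is measurable. The consequence is mainly in the reported level of AUC, AUCnorm and CL; the age-group CL ratio moves by only about 2–5%. Independently of the trapezoid, the printed AUMC tail is wrong, and MRT and Vd cannot be used as defined. This should be corrected, but it does not threaten the trial.

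**What to change.** In SAP 8.1:

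1. Define AUC by linear-up/log-down: (C_n − C_{n+1})·Δt / ln(C_n/C_{n+1}) on declining intervals and the arithmetic mean otherwise. Use the matching form for AUMC, with actual sampling times.
2. Correct the AUMC extrapolation to C_last·t_last/K + C_last/K².
3. Report the prespecified linear AUC and CL next to the new ones. State that the linear formula stood in v1.0, v1.1 and v1.2 and was changed after the Database Review Meeting.
4. Reconcile the 9-h sample between the SAP legend and Protocol v02, and say which schedule applied to which patients.

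The cost is SAP wording and one setting in the non-compartmental software, with no new samples. The drawback is a late change to a long-standing formula for primary-endpoint parameters, which step 3 makes visible to the reader.

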- [4] Before injection as well as 15±5 min after injection
- [5] Blood sampling within 1 h before injection and 15±5 min, 1 h (±5 min), 6 h (±30 min), 24±2 h, and 48±2 h after the end of injection [central laboratory]
- [6] Blood sampling within 1 h before injection as well as 15±5 min after the end of injection [central laboratory]
- [7] If first sample was negative for parvovirus B19 antibodies (sample to be taken before injection) [central laboratory]
- [8] CD4+ count to be repeated if interval between Screening Visit and first injection exceeds 30 days. To be included into the study, the patient's CD4+ count must be >200/μL (i.e., inclusion criterion no. 4).
- [9] Unless obtainable from patient's medical history
- [10] Blood sampling for inhibitor testing should preferably be done at the time of trough FVIII:C levels [central laboratory]

 In case of positive inhibitor results, inhibitor retesting using a second, separately drawn sample should be performed, preferably within 15 days of becoming aware of the positive result.
- [11] Documentation of any thromboembolic events only (to be documented on AE page)

FLOW CHART OF ASSESSMENTS FOR SURGICAL PROPHYLAXIS

	For details	Within	Within	Surgery		POP	Any POP day	End of POP period	3-8 weeks after surgery
	For details, see Section 12 hours before start		3 hours before start	Intra- operatively	End [1]	day 1			
Body weight		х							
Type of surgery		х							 
Location of surgery		х							 
Severity of surgery	7.2.5	х							
Expected duration of surgery		х							
Expected average/ maximum blood loss during surgery	7.2.5	х							 
Actual duration of surgery					Х				
Actual blood loss during surgery					Х				
Administration of IMP			х	(x)	(x)	(x)	(x)	(x)	
FVIII plasma levels	7.2.5		#	(#)	(#)	(#) [2]	(#)	(#)	 
VWF:Ag and VWF:Ac	7.3.5		#			(#) [2]	(#)	(#)	 
Presence of wound hematomas						Х	х	Х	I
Routine safety laboratory	7.3.5	х				(x)	(x)	(x)	
Vital signs	7.3.6	х		х		Х			
Efficacy assessment	7.2.6				S			Н	
Overall efficacy assessment	7.2.6								
Factor VIII inhibitor [3]	7.3.5								X
Narrative of outcome								Х	
Concomitant medications		throughout observation period							
Adverse event monitoring	7.3	throughout observation period							

POP = postoperative, VWF:Ag = von Willebrand factor antigen, VWF:Ac = VWF activity

- () Optional
- # Samples to be taken immediately before (≤ 30 min) and 30±15 min after IMP administration

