3.2 Deviations from the trial protocol with regard to statistical analyses

No deviations from the protocol are planned.

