5.8 Pharmacokinetics / Pharmacodynamics

For Pharmacokinetics and IVR assessments FVIII:C will be measured by both, the chromogenic (CHR) and one-stage assay (OS) and analyzed based on actual IMP potency (refer to section 8.1).

The PK profiles of *Wilate* and the PK parameters derived from them will be summarized by descriptive statistics as well as the presentation of concentration vs. time plots based on the PK set. In the analysis of the PK profiles geometric means and standard deviations will be presented in addition to the arithmetic means and standard deviations.

The following PK parameter will be derived and presented using a non-compartment model:

- Area under the curve (AUC) and AUC normalized for the administered dose (AUC_{norm})
- FVIII in vivo half-life ($T_{1/2}$)
- Maximum plasma concentration (C_{max})
- Time to reach maximum plasma concentration (T_{max})
- Mean residence time (MRT)
- Volume of distribution (Vd)
- Clearance (CL)
- Incremental in vivo recovery (IVR)

Analysis of variance (ANOVA) will be used in an exploratory sense to assess a possible association between ABO blood type, VWF:Ag, and the FVIII:C half-life of *Wilate*.

Incremental IVR will be calculated from FVIII:C plasma levels measured before injection and peak levels obtained in the 15-min post-injection sample using actual IMP potencies. The results of the IVR assessments over time will be analyzed in summary tables for each time point and their differences to baseline along with 95% CIs for the mean differences.

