| C _{max} | Maximal measured concentration after end of IMP infusion (peak concentration) |
| ED | Exposure day = each calendar day the subject received IMP |
| Incremental recovery (IVR) | $IVR = \frac{(C_{max} - C_0) \cdot BW}{D}$ where BW stands for the body weight in kg and D is the dose according to the actual potency of the FVIII concentrate as described in above |
| Labelled potency | Potency of IMP (IU) based on label of vial (IU). Dosing analyses will be based on labelled potency |
| MRT | Mean residence time $MRT = \frac{AUMC}{AUC}$ |
| Success (for bleeding episodes and surgeries) | Excellent or good efficacy rating |

| | |
|----------------------------------|---------------|
| STATISTICAL ANALYSIS PLAN | |
| Protocol No: WIL-30 | |
| Version Number: 1.2 | Page 26 of 27 |
| Date of Issue: 2019-07-08 | |

| Variable | Description |
|-----------|--|
| $T_{1/2}$ | In vivo half-life using linear regression on the terminal phase of the logarithm of the concentration; $T_{1/2} = \frac{\ln(2)}{K}$ (where K , the elimination rate constant, is determined as the slope of the regression line) |
| T_{max} | Time to reach maximum plasma concentration (Timing starts at end of infusion) |
| Vd | Volume of distribution $Vd = CL \cdot MRT$ |

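### SAP 8.1 computes IVR from C_max, while SAP 5.8 and Protocol 9.2.2 use the 15-minute sample; taken literally, 8.1 can raise baseline IVR but not the 3- and 6-month values

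*SAP*

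**What the plan says.** **SAP v1.2, 8.1.** The incremental recovery row reads "IVR = \frac{(C_{max} - C_0) \cdot BW}{D}$ where BW stands for the body weight in kg". The C_max row of the same table reads "Maximal measured concentration after end of IMP infusion (peak concentration" and sets no limit on which sample may supply the maximum.

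**SAP v1.2, 5.8, and Protocol version 02, 9.2.2.** Both calculate IVR from the pre-injection level and "peak levels obtained in the 15-min post-injection sample using actual IMP potencies".

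**Which section applies.** SAP 5.7.2 lists IVR over time among the efficacy endpoints and refers to 5.8 for it. SAP section 5, under Listings, says "Any derived data listed will also be stored permanently and will be calculated as outlined in section 8.1 of this SAP". SAP 3.2 adds "No deviations from the protocol are planned".

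**Sampling.** At the PK Visit the protocol draws post-dose samples at "15±5 min, 1 h (±5 min), 6 h (±30 min), 24±2 h, and 48±2 h after the end of injection", which is five. The SAP flow chart legend in 2.4 adds one at 9 h ("6 h (± 30 min), 9 ± 1 h, 24 ± 2 h"), which makes six. At 3 and 6 months there is one post-dose sample, 15±5 min after injection.

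**Analysis.** IVR at baseline, 3 months and 6 months is a secondary endpoint. It is summarised per time point and as the difference from baseline, with a 95% CI for the mean difference.

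**The concern.** The two rules agree when a visit has a single post-dose sample and can disagree when it has several. Only baseline has several. Under 8.1 as written, the highest of five or six baseline readings would be compared with a single later reading. Measurement error then works in one direction only: a chance high reading at 1 h replaces the 15-minute value, while a chance low one is ignored. The resulting shift in the change from baseline would look like falling recovery in the children, although it comes only from how baseline was defined. What is at stake is how the reported IVR change is read.

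**Working it through.** The documents give no IVR value, half-life or assay precision, so there is no figure of the plan's own to reproduce.

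**Step 1: direction, by algebra.** The difference between the rules is

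IVR(8.1) − IVR(5.8) = (max over samples of C − C_15min) × BW / D.

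- Baseline, 15-minute sample available: the maximum is taken over a set that contains C_15min, so the difference is zero or positive.
- Months 3 and 6: the set has one member, so the difference is exactly zero.
- The change from baseline (later minus baseline) is therefore lower under 8.1, or equal.

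Examples at the protocol's PK dose of 50 IU/kg, with invented concentrations and C_0 = 0.5:

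- 15 min 90, 1 h 85: (90 − 0.5)/50 = 1.79 under both rules.
- 15 min 85, 1 h 92: (85 − 0.5)/50 = 1.69 under 5.8; (92 − 0.5)/50 = 1.83 under 8.1.

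**Step 2: size, under assumptions.** Assumed, not in the documents: half-life t½ of 8 to 15 h, per-sample CV of 5 to 15%, within-visit error correlation ρ of 0, 0.5 or 0.8. The 15-minute reading has true value 1 and the 1 h reading has true value m = exp(−ln2 × 0.75/t½). With normal errors, d = 1 − m and θ = CV × √(1 + m² − 2ρm):

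E[max] = Φ(d/θ) + m·Φ(−d/θ) + θ·φ(d/θ).

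For t½ 10 h, CV 10%, ρ 0.5: m = 0.9493, d = 0.0507, θ = 0.0976, d/θ = 0.519. Then E[max] = 0.698 + 0.9493 × 0.302 + 0.0976 × 0.349 = 1.019, an inflation of 1.9%.

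Simulating all six SAP time points (400,000 draws) agrees with this two-sample form within 0.3 percentage points. Mean inflation of baseline IVR, with 8 h at the low end of each range and 15 h at the high end:

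| CV | ρ = 0 | ρ = 0.5 | ρ = 0.8 |
|---|---|---|---|
| 5% | 0.7–1.4% | 0.2–0.7% | 0.0–0.2% |
| 10% | 2.9–4.0% | 1.5–2.5% | 0.5–1.1% |
| 15% | 5.4–7.0% | 3.2–4.4% | 1.4–2.3% |

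With no measurement error the inflation is zero.

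**Step 3: effect on the interval.** With 8 patients and no true change, the 95% CI for the mean change should lie wholly below zero 2.5% of the time, and under the 15-minute rule it does. Under 8.1, in 100,000 simulated trials per setting, the figure is about 4–13% at ρ = 0, 3–7% at ρ = 0.5 and 2.5–4.5% at ρ = 0.8. These runs have no visit-to-visit variation. Adding an assumed 10% visit SD at 15 h and ρ = 0 lowers the figure from about 7% to about 4% (CV 5%) and from about 11% to about 7% (CV 10%).

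**Step 4: baseline 15-minute sample missing.** Rule 5.8 then has no peak to use, while 8.1 would take a later reading. Without error the 1 h value is lower by 1 − m, which is 6.3% at 8 h and 3.4% at 15 h. The shift reverses and the number of patients analysed differs between the rules.

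**The case against.** The strongest reply is that this is loose notation and the SAP already resolves it. The endpoint list in 5.7.2 sends the reader to 5.8, which says in words which sample supplies the peak for IVR. Section 5.8 refers on to 8.1 only in its sentence on assays and actual potency. Both places speak of a peak, so the specific IVR text can reasonably govern the general symbol, and it agrees with the protocol. An error arises only if someone programs 8.1 and overlooks 5.8.

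Much of this stands. It would be wrong to say that 8.1 governs; the SAP has a pointer each way. But the Listings paragraph does send listed derived data to 8.1, and 8.1 holds the formula. The shared word peak does not settle the matter either, because T_max is reported as a parameter of its own, so the plan allows the maximum to fall at another time.

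A second reply is that the larger figures need uncorrelated errors and no variation between visits. That is correct, and it is why no single size can be claimed.

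A reader might also infer that SAP 5.1.2 makes IVR missing whenever the 15-minute sample is missing, because it says "No further imputations for missing data will be performed". The sentence before it leaves missing points on a PK profile to the WinNonlin algorithms, and baseline IVR is one of the PK parameters derived from that profile. The documents do not settle that case.

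**Conclusion.** The conflict between SAP 8.1 and SAP 5.8 is real and lies within SAP v1.2. It does not depend on protocol version 03, which the SAP v1.2 title page lists but which is not among the documents. The direction is certain when the baseline 15-minute sample is available and sampling follows the schedule: baseline IVR goes up or stays the same, months 3 and 6 do not move, and the change from baseline goes down or stays the same. The size is not determined by the documents. It is about 0 to 7% of mean baseline IVR under the assumed half-life, CV and correlation, and the 7% belongs to one corner (15 h, CV 15%, ρ = 0).

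Severity is minor. The analysis is descriptive, no success criterion rests on it, and all subject data are listed, so the 15-minute IVR can be recovered. A reader might infer that the trial will report a spurious fall in recovery. The documents do not support that: an analyst who follows 5.8 produces no such artefact, and even literal use of 8.1 leaves the result unchanged in any patient whose 15-minute reading is the highest.

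**What to change.** In the IVR row of SAP 8.1, replace C_max by C_15min, defined as FVIII:C in the 15±5 min post-injection sample, at baseline, 3 months and 6 months. Keep the C_max row as a separate PK parameter that does not feed IVR. This brings 8.1 into line with SAP 5.8 and Protocol 9.2.2 and makes the three time points comparable.

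Optionally, state whether baseline IVR is missing when the 15-minute sample is missing. This would be a new rule that the current text does not supply. If it is adopted, a patient without that sample has no IVR change from baseline.

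The cost is one line in the SAP and no new data. Baseline IVR may come out slightly lower than under the C_max formula.
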